#### Exclusion criteria for age matched controls

- Major congenital or chromosomal anomalies
- Inability to tolerate enteral nutrition/ regular cow's milk, breast milk or soy formula

- History of liver/intestinal transplantation
- Active milk protein allergy
- Inflammatory bowel disease
- Multiorgan failure

Inclusion Criteria for glutamine and placebo group of SBS patients (n=36; 18 per site)

- Males and females  $\leq$  12 months of age (corrected for gestational age)
- Patients who have undergone small bowel resection due to complications of or related to NEC, omphalocele, gastroschisis or intestinal atresia with known small bowel length
- Patients who have been PN dependent for more than 42 consecutive days (6 weeks) and currently on TPN at time of enrollment. This would include patients who were off TPN for  $<$  7 consecutive days.
- Patients who have the ability to take partial enteral nutrition of at least 5ml/hr breast milk or elemental formula (Elecare® is the preferred formula at both clinical sites but use of other elemental formula does not exclude the patient) (via gastric or intestinal tube, or orally) to allow the appropriate dose of GLN (0.6 g/kg/day) or placebo (L-alanine)
- Signed informed consent for the use of GLN or placebo obtained

Exclusion Criteria for glutamine and placebo group of SBS patients

- Major congenital or chromosomal anomalies
- Inability to tolerate enteral nutrition that will preclude treatment with enteral GLN or L-alanine placebo for  $>$ 2 consecutive weeks
- Liver/intestinal transplantation
- Multiorgan failure

B. Withdrawal Criteria

1. Patient cannot complete evaluation visit assessments
2. Patient develops any of the exclusion criteria detailed above
3. Patient develops significant hepatic dysfunction (defined as INR  $>$  2.5 or direct serum bilirubin level  $>$  10 mg/dL)
4. Parent(s)/legal guardian are unwilling to administer the GLN or placebo at the required dosage
5. Patient is lost to follow-up
6. Patient has 3 missed study visits
7. It is in the patients best interest

C. Dropouts

Data collected from patients who voluntarily withdraw from the study or who are withdrawn from the study will be included in the final analysis using intent to treat. Patient and control enrollment will continue until 32 patients complete all requested study requirements outlined. The reason for withdrawal will be documented.

D. Stopping Rules

An early stopping rule pending further investigation for this study will be invoked if any of the following adverse events occur:

- The rate of BSI in SBS patients in either the GLN supplementation or the placebo is an absolute 20% higher compared to the historical rate in SBS patients. The rate of catheter associated BSI is assessed monthly in all SBS patients at both CCHMC and the University of Michigan as part of the current clinical improvement process, If the rate of the BSI is higher in either group by 20% then study enrollment will be halted until further evaluation by the Data Safety Monitoring Board (DSMB).
- If two subjects develop the same grade-3 adverse event (including liver function tests, coagulation profile) related to the study medication that is irreversible upon de-escalation (does not reverse after 10 days) or upon discontinuation of the study drug
- Any subject develops a related grade-4 adverse event.

Since this is a double blind placebo control design, the data will only be unmasked by the research pharmacy at the request of the DSMB, if any of the above events occur. The statistician on the DSMB will evaluate the data. The unmasked data will not be revealed to the investigators unless the DSMB requests that the study be terminated.

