#### **VI. Potential Risks**

Potential risks for GLN supplementation:

- Stomach pain - 11%
- Nausea - 22%
- Tenesmus - 11%
- Pancreatitis - 11%
- Constipation - 11%
- Fever - 11%
- Gastric Ulcer - 11%
- Increased irritability - 11%
- Mild skin rash or itching - 11%
- Hyperammonimia in patients with renal and hepatic dysfunction - 11%
- Laryngitis/Pharyngitis - 11%

Other adverse events reported in the product information package

- Gastrointestinal fistula in patients with Crohn's disease - 11%

- Vaginal fungal infections – 11%
- Psychiatric disorders – 11%
- Pyelonephritis – 11%
- Vascular disorders- 11%

Potential risks for L-alanine (placebo):

- Nausea and vomiting - 11%
- Hyperammonimia in patients with renal and hepatic dysfunction - 11%

Potential risks for L-Glutamine and L-alanine

- Hyperosmolality of the feeds leading to increased stool output is a potential side effect of L-Glutamine and L-alanine when added to formula. However, this has not been reported in previous trials. The osmolality of L-glutamine is 310 mosm/kg of water (data provided by Emmaus Medical Inc).

Potential risks for blood draw:

- Occurrence of discomfort and/or a bruise at the site of puncture
- Less commonly, fainting
- The formation of a clot or swelling in the vein and surrounding tissue
- Bleeding from the puncture site
- On rare occasions an infection may develop at the site where the blood is collected

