#### E. Monitoring for toxicity due to GLN

Potential toxicity will be assessed by analyzing clinical and laboratory parameters using the following PN labs (Complete blood count, complete metabolic profile (Renal, Calcium, Phosphorus, Magnesium, Liver panel, Total Protein, Albumin) monthly. Additional blood samples will be done in accordance with current institutional standards for monitoring chronic PN use in infants. Plasma GLN levels will be obtained at baseline and at 6 months.

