#### G. Patient Recruitment and Consenting Process

##### Patient Recruitment

A total of 36 patients with short bowel syndrome (SBS)  $\leq$  12 months of age will be recruited for this study. Of the 36 patients, approximately 24 patients will have colon in continuity and 12 will have colon not in continuity. Assuming a 10% dropout rate, it is expected that 32 SBS patients will complete the study.

For Aim 3 of the study, an additional 12 infants without SBS will be enrolled as the non-SBS control patients. Therefore, a total of 48 patients will be enrolled across the two sites, University of Michigan and Cincinnati Children's Hospital Medical Center.

The study will be explained in detail by the study coordinator or other study team member and the consent form will be reviewed per institutional IRB requirements. These subjects will be recruited through the Division of Gastroenterology, Hepatology, and Nutrition, the Department of Surgery, or the Division of Neonatology. The prospective patients will be identified through the clinical staff within all three divisions working collaboratively. The clinical staff will initially inform potential subjects and families about the research study. The research staff will notify and obtain permission from the patient's primary gastroenterologist, surgeon, or neonatologist before contacting the family.

Subjects who drop out prior to drug initiation may be replaced with new subjects until target enrollment is achieved, as these will not have been given study medication.

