## H. Study Procedures

### **Randomization and study groups**

[figure not shown]
At the baseline visit, SBS subjects will be block randomized in a 1:1 scheme by site and strata (i.e the presence or absence of **colon in continuity**) to receive either L-GLN powder or isonitrogenous, isocaloric placebo [L-alanine (ALA)]. Randomization will be done by the Cincinnati Children's Hospital Medical Center research pharmacist who will not be blinded. Distribution will be done by the site study personnel. The subjects, site investigators and study personnel at all sites will be blinded to the randomization. Since patients will be on breast milk or Elemental formula (Elecare® being the preferred elemental formula at both institutions; however use of other elemental formula does not exclude the patient from the study), the randomization process will take into account whether breast milk or formula is been consumed by the infant. The research pharmacist will make decisions regarding randomization based on the use of formula versus breast milk to ensure adequate distribution within groups.

**Glutamine group:** Infants randomized to the GLN group will receive L-GLN administered enterally at a dose of 0.6g/kg body weight/day (0.3g/kg/dose) in 2 divided daily doses for 6 months (figure 2). GLN will be dissolved in water, breast milk or formula and administered to the subject orally or through their enterostomy tube approximately every 12 hours (twice a day). This can be administered as a bolus or a continuous infusion lasting a maximum of 2 hours. We will use Nutrestore™ (Emmaus Medical, Inc.), a commercially available, FDA approved pure L-GLN product in the study. In the event that this is not available we will use commercially available 100% USP grade L-GLN. The minimal volume L-GLN will be dissolved in at least 10 ml of water, breastmilk or formula.

**Placebo group:** Infants in the placebo group will receive ALA at a dose of 0.6g/kg body weight/day in 2 divided doses (0.3g/kg/day twice a day), exactly as outlined above for the GLN group.

ALA is a non-essential amino acid and will be used as the placebo in this study because it is a nutritional supplement without any known impact on gastrointestinal permeability or local effect on the mucosa or infections. It will balance out the administration of an amino acid (L-GLN) to the study population.

Figure 2: Study design

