## **Recording of Adverse Events**

Adverse event recording will begin after administration of study medication.

Diagnostic and therapeutic non-invasive and invasive (i.e. surgical) procedures will not be reported as adverse events. However, the medical condition for which the procedure was performed must be reported if it meets the definition of an adverse event, unless it is pre-existing (prior to initiating GLN).

Medical conditions/diseases present before starting drug are only considered adverse events if they worsen after starting treatment.

Symptoms of the original or targeted disease are not to be considered adverse events in this treatment. The following symptoms are indicative of underlying disease and will not be reported as adverse events: Malabsorption, growth failure, liver disease and BSI.

Abnormal laboratory values or test results constitute adverse events if they induce clinical signs or symptoms or require therapy. They are to be recorded on the Adverse Events CRF under the signs, symptoms or diagnoses associated with them. CA-BSI will only be reported as an adverse effect if the rate is higher than 20% of what is standard for the center.

As far as possible, each adverse event will be assessed by the Investigator with respect to its duration (start and end dates), the severity grade (mild, moderate, severe, life-threatening, fatal), its relationship to the drug (unrelated, unlikely to be related, possibly, probably and definitely related), the action(s) taken, the outcome (i.e. resolved, resolved with sequelae, continuing), gravity (SERIOUS or NOT SERIOUS), and expected/unexpected on the basis of drug insert.

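### The hepatic withdrawal limits (INR > 2.5 or direct bilirubin > 10 mg/dL) have no matching entry criterion, so an infant already above them can be randomised and dosed

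*Combined protocol and SAP*

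**What the plan says.** **Withdrawal (section IX.B).** Criterion 3 opens "Patient develops significant hepatic dysfunction (defined as INR" and gives the limits as INR > 2.5 or direct bilirubin > 10 mg/dL. Criterion 2 adds "Patient develops any of the exclusion criteria detailed above". Criterion 7 allows withdrawal in the patient's best interest.

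**Entry (section IX.A).** The list headed "Exclusion Criteria for glutamine and placebo group of SBS patients" has four items: major anomalies, feeding intolerance that would prevent dosing for more than two weeks, liver or intestinal transplantation, and multiorgan failure. The five inclusion items cover age, cause of resection, PN dependence, enteral tolerance and consent.

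**Randomisation (section IX.H).** "At the baseline visit, SBS subjects will be block randomized in a 1:1 scheme by site and strata".

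**Known risk (section VI).** "Hyperammonimia in patients with renal and hepatic dysfunction - 11"% appears under glutamine and again under L-alanine.

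**Monitoring (section IX.E).** The PN labs include "Liver panel, Total Protein, Albumin) monthly", with further samples according to institutional PN standards. Neither INR nor ammonia is named in that list.

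**Recruitment (section IX.G).** "The research staff will notify and obtain permission from the patient's primary gastroenterologist, surgeon, or neonatologist before contacting the family".

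**Adverse events (section XII).** Liver disease is treated as part of the underlying condition and is not reported as an adverse event. However, "Abnormal laboratory values or test results constitute adverse events if they induce clinical signs or symptoms or require therapy".

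**The concern.** By writing criterion 3 the sponsor has decided that an infant above these limits should not stay in the trial. The entry criteria do not apply the same decision at the door. Both study products are amino acids for which the protocol itself lists a hazard in hepatic dysfunction, so assignment to placebo does not remove the concern. All eligible infants have been PN dependent for more than 42 days, and section XII lists liver disease as a feature of the underlying condition, so the case is not far-fetched.

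Criterion 3 also handles such an infant awkwardly. Because it says *develops*, a strict reading may not cover someone who was above the limit before the first dose. Read as *has*, it removes the infant only after dosing that could have been avoided. What is at stake is avoidable exposure of a vulnerable infant and an eligibility rule that does not match the withdrawal rule.

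**Working it through.** The plan states no figure on this point to reproduce. The check is a count of criteria followed by a comparison of sections.

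**1. Count the entry criteria for infants with short bowel syndrome (section IX.A).**

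| Criterion | Liver limit stated? |
|---|---|
| Inclusion 1: age up to 12 months, corrected | No |
| Inclusion 2: resection for a listed cause | No |
| Inclusion 3: PN dependent more than 42 days | No |
| Inclusion 4: at least 5 ml/hr enterally | No |
| Inclusion 5: consent | No |
| Exclusion 1: major anomalies | No |
| Exclusion 2: enteral intolerance | No |
| Exclusion 3: liver or intestinal transplantation | No INR or bilirubin limit |
| Exclusion 4: multiorgan failure | No; undefined, and does not reach isolated hepatic dysfunction |

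5 + 4 = 9 criteria; 0 of 9 state a limit on INR, bilirubin or liver function.

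**2. Trace an infant with direct bilirubin above 10 mg/dL, no transplant and no multiorgan failure.** All nine criteria can be met. Section IX.H randomises at the baseline visit, and no rule in that section ties a liver result to randomisation. Dosing can start.

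**3. Set each existing check beside the question of whether it stops entry.**

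| Check | Section | Limit at entry? |
|---|---|---|
| Treating physician's permission | IX.G | No; governs contact with the family |
| History and examination at baseline | IX.H | No |
| Monthly liver panel | IX.E | No; not linked to eligibility |
| Safety calls from day 15 (± 7 days) | IX.H | No; adverse events and symptoms after dosing starts |
| Drug withheld in multiorgan failure or vasopressor use | IX.H | No; not triggered by isolated hepatic dysfunction |
| Stopping rule naming liver and coagulation tests | IX.D | No; acts on adverse events |
| Data Safety Monitoring Board (DSMB) tables of coagulation and liver profiles | XI | No; review after treatment starts |
| Discontinuation for related reactions above grade 3 | XII | No |
| Withdrawal criteria 3 and 7 | IX.B | No; act after entry |

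**4. Check that the statistics are untouched.** Exact enumeration of the one-sided Fisher test (16 per group, 75% versus 30%, 10% level) gives 85.7% power, in line with the at least 85% stated under Sample size. Also 32 / (1 − 0.10) = 35.6, which rounds up to the stated 36. Adding an exclusion changes neither calculation. It would make the count in step 1 one of ten.

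**The case against.** The strongest case on the other side is that the affected group is narrow and watched closely. The infant must exceed a severe limit, have no transplant or multiorgan failure, tolerate at least 5 ml/hr enterally, and be under a clinician who manages the PN and must agree before the family is approached. That clinician will usually know the liver results. Coagulation data are expected too, since the stopping rule and the DSMB tables both refer to them. An investigator who sees a value above the limit can use criterion 7 whatever *develops* means, and criterion 2 uses the same verb. Broad hepatic entry in a pilot of 36 infants may even be deliberate, although the documents give no rationale either way.

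Most of this stands, and it lowers the likely frequency. It does not close the gap, because every one of these checks is either discretionary or acts after randomisation.

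Two stronger readings fail:
- A reader might infer from the study procedures table that no liver tests exist at baseline, because none is shown. That table also omits the monthly panel that section IX.E requires, so it is not a complete laboratory schedule.
- A reader might infer that hyperammonaemia in such an infant would go unrecorded because liver disease is not reported as an adverse event. Section XII still captures abnormal results that cause symptoms or need treatment.

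**Conclusion.** The gap is real and small. Withdrawal criterion 3 sets a hepatic limit, no entry criterion does, and the plan followed as written allows an infant above that limit to be randomised and dosed until a clinician acts. The conclusion rests only on the text of sections VI, IX and XII. The number of infants affected cannot be derived from the documents and may be zero. This is a cheap improvement to eligibility and safety, not an error in the analysis.

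Some larger claims might be inferred and are not supported:
- **Size of harm.** Multiplying the daily dose by time on product would not measure harm. The date of the first panel is not stated, a long exposure needs every safeguard to fail, and the documents give no toxicity threshold. The 11% attached to hyperammonaemia is the figure given for almost every listed event, so it is not a specific estimate of this risk.
- **Purpose of the limit.** The protocol does not say that criterion 3 was set to prevent hyperammonaemia. The link between sections VI and IX.B is a reasonable inference only.
- **A pattern across withdrawal conditions.** The other medical withdrawal conditions are barred at entry by construction, because criterion 2 re-imports the exclusions. Counting them adds no evidence.
- **Effect on the results.** With no prevalence given, no effect on power, the 10% dropout allowance or the primary comparison can be claimed. Section IX.C also keeps withdrawn infants' data in the intent-to-treat analysis.

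**What to change.** Add one exclusion for infants with short bowel syndrome: direct bilirubin > 10 mg/dL, or INR > 2.5 where a recent value is available. Check it before randomisation on the most recent routine PN labs within a stated window. Thirty days would match the monthly panel, but that choice is open to the sponsor. Reword criterion 3 from *develops* to *has or develops*, so that it also covers an infant whose raised value predates the first dose but comes to light only later.

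The cost is one exclusion line and one wording change. The threshold is the sponsor's own, and using labs already drawn for PN care means no extra blood. There are two downsides. The eligible pool becomes slightly smaller, though only by infants the plan already regards as unsuitable to continue. A raised INR that nobody has measured would still be missed, because section IX.E does not list INR and the other references to coagulation give no schedule.

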### XII. Adverse Events

An adverse event (AE) is any untoward medical occurrence in a patient participating in this trial. An adverse event can be an unfavorable and/or unintended sign (including an abnormal laboratory finding), symptom, syndrome or disease associated with or occurring during the use of an investigational product whether or not considered related to the investigational product.

A serious adverse event (SAE) is one that:

1. results in death
2. is life threatening
3. requires an inpatient hospitalization or prolonged existing hospitalization
4. is a persistent or significant incapacity or substantial disruption of ability to conduct normal life functions
5. is a congenital anomaly/birth defect
6. is an event that does not meet the above criteria but may jeopardize the patient or may require medical or surgical intervention to prevent one of the outcomes listed above.

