### Grading (Severity) of Adverse Events

Each adverse event will be graded to describe its intensity according to the Severity scale listed for each AE found on the NCI's Common Terminology Criteria for Adverse Events Version 4.0.

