#### Relationship to Drug

For all adverse events that occur while the patient is on drug, the relationship to the drug must be assessed by the Investigator using the following scale:

- 1 = not related
- 2 = unlikely
- 3 = possibly related
- 4 = probably related
- 5 = definitely related

For Grade > 3 adverse reactions which are possibly (3), probably (4) or definitely (5) related to the drug, study medication should be discontinued as described above.

Please note: For safety data analysis, not related and unlikely are considered "not attributable;" possible, probable and definite are considered "attributable." Assessment of relationship to drug must be carried out by the Investigator according to the 5-point scale above.

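### The stopping rules name liver and coagulation results, but the adverse-event sections conflict on whether a symptom-free, untreated result counts

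*Combined protocol and SAP*

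**What the plan says.** Section IX.D (Stopping Rules) lists three events that pause the trial pending investigation. The first concerns the BSI rate. The second reads "If two subjects develop the same grade-3 adverse event (including liver function tests, coagulation profile) related to the study medication", and requires that the event fail to reverse, either within 10 days of de-escalation or on stopping the drug. The third is any related grade-4 adverse event in one subject, with no irreversibility condition.

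Section XII (Adverse Events) opens with a broad definition: "An adverse event can be an unfavorable and/or unintended sign (including an abnormal laboratory finding". It sets no symptom or treatment condition.

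The subsection Recording of Adverse Events is narrower: "Abnormal laboratory values or test results constitute adverse events if they induce clinical signs or symptoms or require therapy". Results that qualify are entered under the sign, symptom or diagnosis that goes with them. The same subsection lists manifestations of the underlying disease that "will not be reported as adverse events: Malabsorption, growth failure, liver disease and BSI". On pre-existing conditions it says "Medical conditions/diseases present before starting drug are only considered adverse events if they worsen after starting treatment". For bloodstream infection it adds a way back in: "CA-BSI will only be reported as an adverse effect if the rate is higher than 20% of what is standard for the center".

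Grading and causality both start from an adverse event: "Each adverse event will be graded to describe its intensity according to the Severity scale listed for each AE" and "For all adverse events that occur while the patient is on drug, the relationship to the drug must be assessed by the Investigator".

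**The concern.** The two adverse-event triggers work only if a result passes through three steps: it is recorded as an adverse event, graded, and judged related. The stopping rule names liver and coagulation tests, so the sponsor evidently meant such results to count. The recording rule can remove some of them at the first step, after which nothing obliges anyone to take the other two.

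The grade-3 rule needs the same event in only two subjects, and the grade-4 rule needs one, so a single unrecorded result can decide whether a rule is met. The two sites could also apply the recording rule differently. The triggers matter beyond the pause itself: section IX.D makes unmasking a step taken at the DSMB's request if one of the listed events occurs.

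**Working it through.** The plan states no figure on this point, so there is none to reproduce. The check sets the sections side by side for one test case: a liver or coagulation result of CTCAE grade 3 or higher, new since starting drug, with no symptoms and no therapy given.

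| Step | Section | Outcome for the test case |
|---|---|---|
| Is it an adverse event? | XII, opening definition | Can be |
| Is it an adverse event? | XII, Recording of Adverse Events | Not on the natural reading; no sign, symptom or diagnosis to enter it under |
| Is it graded? | XII, Grading (Severity) | Required only if it is an adverse event |
| Is it assessed for relatedness? | XII, Relationship to Drug | Required only if it is an adverse event |
| Does it count? | IX.D | Tests of this kind are named in the grade-3 rule, but only as adverse events with a grade and a judgement of relatedness |

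**Does any text say which rule governs?** I found none. Section IX.D does not refer to the recording rule, and the recording rule does not refer to liver or coagulation results under IX.D. For BSI, which is also on the list of unreported conditions, the recording rule supplies an exception with a 20% threshold that parallels the BSI trigger. It supplies none for liver or coagulation results.

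**Do other provisions feed the count?**
- Section XI gives the DSMB tabulations of coagulation studies and liver profiles, with adverse-event frequency as a separate item. It also gives a cumulative listing of withdrawals, dose adjustments and serious adverse events. Safety data go to members about every 6 months, or more often if the chair asks. These show results to the DSMB but are not linked to the trigger.
- Section IX.B withdraws a patient with INR above 2.5 or direct bilirubin above 10 mg/dL. This acts on the individual and is not linked to the trigger either.
- Section IX.E schedules a monthly liver panel. Its list does not name coagulation tests, so those depend on institutional practice.

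**Size.** The grade-3 trigger is 2 of the 36 SBS subjects: 2/36 = 5.6%. The grade-4 trigger is 1 of 36: 1/36 = 2.8%. If exactly two subjects have the same qualifying grade-3 event and one is not recorded, the count is 2 − 1 = 1 and the rule is not met. These figures describe the thresholds, not the effect. The documents give neither the rate of such results nor the share that would go unrecorded, so I make no estimate.

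**The case against.** There is a serious case that this is loose drafting with little consequence.

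- **The recording rule says if, not only if.** The same subsection writes the exclusive word where it means it ("Medical conditions/diseases present before starting drug are only considered adverse events if they worsen after starting treatment"; "CA-BSI will only be reported as an adverse effect if the rate is higher than 20% of what is standard for the center"). This stands in part: the limiting reading is not compelled. But if the condition excludes nothing, the sentence adds nothing to the general definition, and two sites could fairly read it in two ways.
- **The parenthesis in the stopping rule is a special inclusion that overrides a general recording rule.** That is a reasonable reading, but the text does not adopt it. Nor does it say who would grade and attribute a result that the recording rule leaves off the form.
- **The liver-disease exclusion creates no conflict.** A reader might infer that it bars every liver result from the trigger. The documents do not support that: the exclusion is framed as covering manifestations of the underlying disease, the trigger counts only drug-related events, and worsening of a pre-existing condition is an adverse event. The exclusion adds ambiguity but can be reconciled. The conflict rests on the laboratory-value rule.
- **Irreversibility means someone has already acted.** An event that meets the grade-3 rule has been through de-escalation or discontinuation, and this should appear in the DSMB listing. This narrows the gap considerably. It does not close it. A result not treated as an adverse event need not prompt the de-escalation that tests reversibility. De-escalation is not said to be therapy for the purposes of the recording rule. The grade-4 rule has no such condition.
- **The DSMB sees the laboratory data anyway.** True, and this is the main reason the point is minor.

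**Conclusion.** The point holds in a limited form. The documents conflict on whether a symptom-free, untreated liver or coagulation result of grade 3 or higher is recorded, graded, assessed for relatedness and counted under section IX.D. Such results may be missed or counted inconsistently.

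Two stronger conclusions are tempting. One is that a liver or coagulation signal would go unseen. The documents do not support this, given the DSMB tabulations, the listing of withdrawals and dose adjustments, and the hepatic withdrawal criterion. The other is a probability that the rule fails to fire. Any such number would need an event rate and a recording probability that the documents do not give.

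Severity is minor. Confidence is moderate, because the conclusion rests on reading the recording rule's condition as limiting, which is natural but not forced.

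**What to change.** Add one sentence to Recording of Adverse Events in section XII: *For the stopping rules in IX.D, any liver or coagulation result that is CTCAE v4.0 grade 3 or higher and at least one grade above the subject's baseline is recorded as an adverse event, with or without symptoms or therapy, graded and assessed for relatedness, despite the liver-disease exclusion.*

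The words 'or higher' are needed because the grade-4 trigger also counts adverse events. The one-grade step keeps fluctuation within a grade from generating repeated entries in infants who start with abnormal values. The irreversibility condition in the grade-3 rule should stay as it is.

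The cost is one sentence of amendment and one instruction on the adverse-event form, with no extra blood draw. The downside is somewhat more adverse-event recording and possibly more DSMB reviews, since liver abnormalities may be frequent in PN-dependent infants. The sentence does not widen detection: coagulation results stay limited to those drawn under institutional practice, because the monthly panel in section IX.E does not list them.
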